8.2.6 Patient Diary

Xevinapant will be dispensed by the medical staff or pharmacist of the investigational sites. The participant will receive xevinapant on an outpatient basis.

On days of PK sampling, C1D2, C1D9, and C2D2 participants must take their doses at the hospital, where the administration of xevinapant will be supervised and recorded by the medical staff both in the eCRF and in the patient's diary. In addition, time of last dose taken prior to xevinapant PK collection (i.e. at C1D1, C1D8, C2D1) needs to be recorded in the participant's diary, if taken at home, and all need to be reported in the eCRF.

The treatment schedule of xevinapant is presented in [Table 2](#) and

[Table 3](#). Participants will be instructed by the medical staff on how to self-administer xevinapant at home. The participant should inform the medical staff of any missed or delayed doses.

The diary will be dispensed to the participants according to the schedule presented in [Table 2](#). They will be instructed on how to record xevinapant administration (i.e. date and time of the xevinapant intake should be recorded in the diary).

Participant should record any skipped or miss-timed doses in their diary.

Participants will be asked to bring the diary with them to their study visits. The diary will be collected and reviewed by site staff after the completion of each visit.

8.2.7 Audiometry

An audiometry must be performed at screening. In addition, hearing clinical evaluation and audiometry should be performed if clinically indicated at C1D8, C1D15, C2D1, C2D8, C2D15, C3D1, and at any time as per institutional or national guidelines. During the follow-up period, an audiometry is to be performed only if clinically indicated, as per institutional or national guidelines.

8.3 Adverse Events, Serious Adverse Events, and Other Safety Reporting

- The definitions of an AE and SAE are in [Appendix 7](#).
- The Investigator and any qualified designees (e.g. Subinvestigators) are responsible for detecting, documenting, and recording events that meet the definition of an AE or SAE. The Investigator remains responsible for following up all AEs, considered related to the study intervention or study procedures, or that caused the participant to discontinue the study intervention or study, as specified in Section [8.3.2](#).
- Requests for follow-up will usually be made via the Sponsor or CRO-designated study team member, although in exceptional circumstances the global patient safety department may contact the Investigator directly to obtain further information or to discuss the event.
- The method of recording, evaluating, and assessing causality of AEs and SAEs and the procedures for completing and transmitting SAE reports are in [Appendix 7](#)
- All AEs and SAEs will be collected from the signing of the ICF until the EOS/follow-up visit at the timepoints specified in the SoA (Section [1.3](#)). Beyond this reporting period, any new unsolicited SAEs that the Investigator spontaneously reports to the Sponsor will be collected and processed.
- All SAEs will be recorded and reported to the Sponsor or designee immediately and under no circumstance will this exceed 24 hours, as indicated in [Appendix 7](#). The Investigator will submit any updated SAE data to the Sponsor within 24 hours of it being available using the same procedure that was used for the initial report.
- Investigators are not obligated to actively solicit information on AEs or SAEs after the end of study participation. However, if the Investigator learns of any SAE, including a death, at any time after a participant has been discharged from the study, and he/she considers the event to be reasonably related to the study intervention or study participation, the Investigator will promptly notify the Sponsor.

8.3.1 Method of Detecting Adverse Events and Serious Adverse Events

At each study visit, the participant will be queried on changes in their condition.

Care will be taken not to introduce bias when detecting AEs and/or SAEs. Open-ended and non-leading verbal questioning of the participant is the preferred method to inquire about AE occurrences.

The method of recording, evaluating, and assessing causality of AEs and SAEs and the procedures for completing and transmitting SAE reports are in [Appendix 7](#).

AE data will be obtained by querying the participant and checking the AESI list (Section [8.3.7](#)) and will be based on the physical examination. Particular focus should be on the gastrointestinal system, hepatobiliary system, kidneys, pancreas, mucosae in head neck area, skin, and eyes.

Complete, accurate, and consistent data on all AEs experienced for the duration of the reporting period (defined in below sections) will be reported on an ongoing basis in the appropriate section of the eCRF.

All SAEs must be additionally documented and reported using the appropriate report form as specified in [Appendix 7](#)

8.3.2 Follow-up of Adverse Events and Serious Adverse Events

After the initial AE/SAE report, the Investigator is required to proactively follow each participant at subsequent visits/contacts. All SAEs, and AESIs (as defined in Section [8.3.7](#)), will be followed until resolution, stabilization, the event is otherwise explained, or the participant is lost to follow-up (as defined in Section [7.3](#)). Reasonable attempts to obtain this information will be made and documented. It is also the Investigator's responsibility to ensure that any necessary additional therapeutic measures and follow-up procedures are performed. Further information on follow-up procedures is in [Appendix 7](#).

8.3.3 Regulatory Reporting Requirements for Serious Adverse Events

- Prompt notification by the Investigator to the Sponsor of an SAE (particularly life-threatening and deaths) is essential so that legal obligations and ethical responsibilities toward the safety of participants and the safety of a study intervention under clinical investigation are met.
- The Sponsor has a legal responsibility to notify both the local regulatory authority and other regulatory agencies about the safety of a study intervention under clinical investigation. The Sponsor will comply with country-specific regulatory requirements relating to safety reporting to the regulatory authority, IRB/IEC, and Investigators.
- Individual Case Safety Reports will be prepared for SUSARs according to local regulatory requirements and Sponsor policy and forwarded to Investigators within 15 days.
- An Investigator or Subinvestigator who receives an Individual Case Safety Report describing a SUSAR or other specific safety information (e.g. Emerging Safety Issue Report, summary or listing of SAEs/SUSARs) from the Sponsor will read it and confirm completion of this activity. This information will be filed in the Investigator's Site File, and the IRB/IEC will be notified, if appropriate, according to applicable local laws/regulations and site SOPs.
- In this global clinical multicenter study, the Sponsor is in the best position to determine an unanticipated problem (as defined in US Regulations 21 CFR 312.66). The Sponsor will immediately notify all Investigators of findings that could adversely affect the safety of participants, impact the conduct of the study or alter the IRB's approval/favorable opinion to continue the study. An unanticipated problem is a serious adverse event that by its nature, incidence, severity, or outcome has not been identified in the current version of the risk analysis report, specified in Section [2.3](#).

Details on SAE reporting is specified in [Appendix 7](#).

8.3.4 Pregnancy

- Details of all pregnancies in participants and participant's partners will be collected after the start of study intervention and until 6 months after the last administration of chemotherapy or 3 months after last dose of xevinapant corresponding to time needed to eliminate study intervention(s) (e.g. 5 terminal half-lives) after the last dose of study intervention.
- If a pregnancy is reported, the Investigator will record the pregnancy information in the CRF which will be reported to the Sponsor within 24 hours after awareness of the participant's or partner's pregnancy (after obtaining the necessary signed partner's informed consent).
- While pregnancy itself is not considered to be an AE or SAE, any pregnancy complication, or elective termination of a pregnancy will be reported as an AE or SAE. Adverse pregnancy outcomes (e.g. spontaneous abortion, fetal death, stillbirth, congenital anomalies, ectopic pregnancy) are considered and reported as SAEs. A spontaneous abortion (occurring at < 22 weeks gestational age) or stillbirth (occurring at > 22 weeks gestational age) is always considered to be an SAE and will be reported as such.
- The participant /partner will be followed to determine the outcome of the pregnancy. The Investigator will collect follow-up information on the participant/ partner and the neonate, and the information will be forwarded to the Sponsor. Generally, follow-up will not be required for longer than 6 to 8 weeks beyond the estimated delivery date for a healthy newborn. In case of a congenital anomaly or other illness of the newborn, follow-up will continue until the illness has resolved or there is a definite outcome of the event.
- Any post study pregnancy related SAE considered reasonably related to the study intervention by the Investigator will be reported to the Sponsor as specified in Section 8.3.3. While the Investigator is not obligated to actively seek this information in former study participants /partner, they may learn of an SAE through spontaneous reporting.
- Any participant who becomes pregnant while participating in the study will discontinue study intervention.

8.3.5 Cardiovascular and Death Events

No dedicated collection of cardiovascular TEAEs is planned for this study. Potential cardiovascular adverse events will be recorded according to standard TEAE documentation and reporting process. Death will not be collected as SAE but only be recorded as outcome of a TEAE.

8.3.6 Disease-Related Events and/or Disease-Related Outcomes Not Qualifying as AEs or SAEs

The following DREs are common in participants with SCHNN and can be serious/life-threatening:

- Progression of the underlying SCCHN.
- Because these events are typically associated with the disease under study, they will not be reported according to the standard process for expedited reporting of SAEs even though the event may meet the definition of an SAE. These events will be recorded as part of the secondary endpoint.

- However, the event will be recorded and reported as an AE/SAE (instead of a DRE) as defined in [Appendix 7](#).

8.3.7 Adverse Events of Special Interest

All AESIs during the treatment period should be recorded promptly to the Sponsor and in the eCRF within 24 hours. Nonserious AESIs should be reported on an AESI form. In addition, serious AESIs must be documented on an SAE form. All SAEs must be reported as specified in [Appendix 7](#).

Based on emerging safety data collected during this and other xevinapant studies, changes to the AESI list might be required. Should this be the case, an updated list will be included in the Investigator's Brochure at the regular annual update. Thus, Investigators should consult the latest version of the Investigator's Brochure when assessing the need to report an AESI.

The AESIs for this study are defined below according to study period (also refer to the IB for any updates).

For this study, AESI(s) include the following as listed in Section [8.3.7.1](#) and Section [8.3.7.2](#).

8.4 Pharmacokinetics

8.4.1 Blood Sampling and Bioanalysis

- Samples are collected only where allowed by local law/regulations.

On all PK days (C1D2, C1D9, and C2D2; [Table 4](#)) participants take xevinapant at the hospital to ensure predose collection for xevinapant PK at the predose timepoint.

Whole blood samples of approximately 3 mL per collection for measurement of plasma concentrations of xevinapant (including metabolite[s], such as D-1143-MET1) will be collected.

Collection times are specified in the Pharmacokinetic Assessments SoA ([Table 4](#)). The actual date and time (24-hour clock time) of each sample collection will be recorded in the eCRF to calculate actual time elapsed since the prior dose administration. On PK days, record time of oral xevinapant dose, time of start and end of cisplatin infusion, and time of PK sampling for each sample in eCRF. In addition, record time of previous dose prior to PK sampling day (such as dose taken on C1D1, C1D8, C2D1) in eCRF or patient diary if taken at home. Volumes of doses taken on PK sampling days and prior dose needs to be recorded in eCRF (C1D1, C1D2, C1D8, C1D9, C2D1, and C2D2).

- The quantification of xevinapant in plasma will be performed using a validated bioanalytical method. In addition, metabolite(s) (such as D-1143-MET1) will be measured. Concentrations will be used to evaluate the PK of xevinapant and D-1143-MET1 via population PK approaches.
- Remaining samples collected for analyses of xevinapant (including metabolite[s] such as D-1143-MET1) may also be used to evaluate safety or efficacy related to concerns arising during or after the study, including safety laboratory assessment and cisplatin concentrations.

Details on processes for collection and handling of these samples are in the Laboratory Manual. Retention time and possible analyses of samples after the end of study are specified in the respective ICF.

8.4.2 PK Parameters

The following PK parameters will be calculated, when appropriate:

Symbol	Definition
C_{trough}	The concentration observed at the end of a dosing interval immediately before next dosing (xevinapant)

- Other PK parameters might be added based on emerging data. Details will be in the IAP. Concentration data may be used for integrated data analyses across studies, such as population PK and CCI [REDACTED], efficacy, and/or safety analyses and reported separately from the main CSR.

8.5 Genetics and/or Pharmacogenomics

Not applicable

8.7 Immunogenicity Assessments

Not applicable

8.8 Health Economics

Not applicable

9 Statistical Considerations

Details of these analyses will be specified in the IAP.

9.1 Statistical Hypotheses

No formal statistical hypothesis will be tested, as the study is designed to be exploratory.

9.2 Sample Size Determination

A total of approximately 40 participants will be treated with study intervention such that approximately 38 DLT-like evaluable participants are anticipated to be obtained. Participants who prematurely discontinue, for reasons other than DLT-like events earlier than 5 weeks after start of treatment, may be replaced.

The tolerability will be assessed using the DLT-like criteria (Section 8.2.5.1) during the initial 5 weeks for each participant (DLT-like assessment period). The SMC will review the safety data. If the incidence of DLT-like adverse events is $< 40\%$ at the SMC review with 18 participants and the primary analysis, treatment will be determined to be tolerable. If the incidence of DLT-like adverse events is $\geq 40\%$ at the SMC review with 18 participants and the primary analysis, SMC will make a recommendation based on a comprehensive assessment of all available data. In the SMC review with 6 and 12 participants or any in non-pre-specified SMC review, the occurrence of DLT-like

events will be evaluated qualitatively, but the tolerability of the treatment will not be determined using the 40% threshold of DLT-like events due to the small sample size.

The threshold of 40% is based on the previous DLT-like event rate of 33% observed in the xevinapant arm in Study CCI [REDACTED]

[REDACTED] In general, a threshold of 30% is used in early oncology first in human studies; however, 40% is considered appropriate for this study, because the cisplatin, and IMRT based backbone treatment is known to already have a certain level of toxicity. CCI [REDACTED]

The sample size is determined by having a set of DLT-like adverse event evaluable participants of a size, which provides an estimated incidence proportion of DLT-like adverse events below the threshold of 40% with a likelihood of 80%, if the true underlying incidence proportion would be at 30%. Based on the simulation study, the actual such probability at SMC with 18 participants is 85.9% and actual limit of observed DLT-like events is 7 events (38.9%, CI: 17.3; 67.3). The following table summarize the results for entire study (i.e. probability of both SMC and PA result in a proportion below 40%) with varying sample size:

Table 15 Sample Size Calculation

N	Probability		
	x (%)	95% CI	P(X ≤ x p = 0.3)
37	14 (38.8)	[17.3, 67.3]	81.0%
38 (selected)	15 (39.5)	[22.5, 57.5]	83.0%
39	15 (39.5)	[24.0, 58.8]	82.0%
40	15 (38.5)	[23.4, 57.6]	80.6%

N=total of DLT-like evaluable participants, x=observed DLT-like adverse events (here limit for x/N ≤ 0.4), p=true underlying incidence proportion for DLT-like adverse events, CI=Exact (Clopper-Pearson) confidence interval, P(X ≤ x | p = 0.3)=probability to observe a DLT-like adverse event incidence proportion below 40%).

9.3 Analysis Sets

The analysis sets are specified below.

Table 16 Analysis Set

Analysis Set	Description
SCR	All participants who provided informed consent, regardless of the study intervention status in the study.

Analysis Set	Description
DLT	All participants who were administered any dose of any study intervention and meet at least 1 of the following criteria: 
Experienced at least one DLT like event confirmed by the SMC during the DLT like assessment period or for whom the composite ICE strategy led to a DLT like event, regardless of the administered number of doses of study intervention/completion in the DLT like assessment period.Received at least 60% of the planned cumulative dose of xevinapant and cisplatin during the DLT-like assessment period, regardless of the completion in the DLT-like assessment period.
FAS/SAF	All participants who were administered any dose of any study intervention.
PK	All participants, who receive at least 1 dose of xevinapant, have no relevant protocol deviations or important events affecting PK, and provide at least 1 measurable postdose concentration.

DLT=dose-limiting toxicity, FAS=full analysis set, PK=pharmacokinetic, SAF=safety, SCR=screening.

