It is planned to enroll approximately 40 adult participants of all sexes such that approximately 38 DLT-like evaluable participants are anticipated to be obtained. In case participants drop out of the study for reasons other than DLT-like events earlier than 5 weeks after start of treatment, additional participants may be enrolled to ensure 38 evaluable participants in the DLT analysis set.

The primary analysis is planned when at least 38 participants meet at least 1 of the following criteria (see Section [9.4.4](#)):

- Experience at least 1 DLT-like event, regardless of the administered amount of study intervention/completion in the DLT-like assessment period.
- Receive at least 60% of the planned cumulative dose of xevinapant and cisplatin during the DLT-like assessment period and either complete the DLT-like assessment period or discontinue study or study treatment for non-AE-related reasons.

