4.4 End of Study Definition

The primary completion date is defined as the data cut-off date for the primary analysis when a total of 38 participants have completed the 5 weeks DLT-like assessment period or discontinued earlier and are not replaced. After the primary completion date, follow-up continues until the end of study defined below.

The end of the study is defined as the date of the last visit of the last remaining on-study participant. All remaining participants will be taken off study once a decision to end the study has been made or the last remaining on-study participant reaches their 18-month post-first treatment visit, whichever occurs earlier. At this timepoint, all participants who have not previously discontinued from the study prematurely will undergo the EOS assessments as specified in Section 1.3 and will be considered as having completed the study.

A participant has completed the study if they have completed all study parts, including the last visit or the last scheduled procedure shown in Section 1.3. Participants will receive the appropriate follow-up treatment per institutional standards.

5 Study Population

The study will enroll unresected LA SCCHN participants who are eligible for cisplatin-based chemoradiotherapy.

The criteria in Sections 5.1 and 5.2 are designed to enroll only individuals who are appropriate for the study; thereby, ensuring the study fulfills its objectives. All relevant medical and nonmedical conditions are considered when deciding whether an individual is suitable for this study.

Prospective approval of protocol deviations to inclusion and exclusion criteria, also known as protocol waivers or exemptions, is not permitted.

Before performing any study assessments that are not part of the individual's routine medical care, the Investigator will confirm that the individual has provided written informed consent, as indicated in [Appendix 5](#).

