Study intervention restart or rechallenge after liver clinical safety laboratory test stopping criteria are met by any participant in this study are not allowed.

7.2 **Participant Discontinuation/Withdrawal from the Study**

- A participant may discontinue from the study at any time, at their own request or at the discretion of the Investigator for safety, behavioral, compliance, or administrative reasons (e.g. disruption of operations due to natural disasters, interruption of laboratory, or facility accreditation, participant moving to another country, resignation of key staff").
- At the time of study discontinuation, if possible, a discontinuation visit will be conducted, as listed in the SoA. The SoA specifies the data to collect at study discontinuation and follow-up, and any additional evaluations that need to be completed.

- If the participant revokes consent for the study, any data collected up to that point may still be used, but no future data can be generated, and any biological samples collected will be destroyed.
- If a participant requests the destruction of any biological samples still remaining, the Investigator will document this in the site study records and inform the Sponsor. The samples will be destroyed.
- Participants may voluntarily withdraw consent for study participation at any time. If such withdrawal occurs, every effort must be made by the Investigator to determine the primary/underlying reason for this decision which must be recorded as reason in the form in the eCRF i.e. if the underlying reason for the decision is toxicity (e.g. AE) this must be recorded as such and the Investigator has to follow-up with the participant until the AE is resolved.
- Premature discontinuation from the study can also be triggered by:
 - Participant lost to follow-up (Section 7.3)
 - Death
 - Disease progression
 - Early study termination by the Sponsor, SMC, the Investigator, the IEC/IRB, or the Regulatory Agencies
- Should a participant be withdrawn from the study, EOS assessments must be performed prior to any further therapeutic intervention, whenever possible. Results of these assessments must be recorded in the eCRF, together with a description of the reasons for study discontinuation.

Participants who prematurely discontinue, for reasons other than DLT-like events earlier than 5 weeks after start of treatment, may be replaced.

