#### Dose Limiting Toxicity Analysis Set (DLT)

All participants who were administered any dose of any study intervention and meet at least 1 of the following criteria:

- Experienced at least one DLT like event confirmed by the SMC during the DLT like assessment period or for whom the composite ICE strategy led to a DLT like event, regardless of the administered number of doses of study intervention/completion in the DLT like assessment period. ICE strategy is defined as

- Discontinuation/interruption/delay of xevinapant/cisplatin treatment [REDACTED] in DLT-like assessment period) due to reasons other than treatment-related AE (composite strategy: to be considered as DLT-like event)
- [REDACTED] during the DLT-like assessment period due to reasons other than treatment-related AE (composite strategy: to be considered a DLT-like event)
- [REDACTED] of xevinapant and cisplatin during the DLT-like assessment period, regardless of the completion in the DLT-like assessment period.

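### An event-free participant who leaves the study from about Day 24 is analysed as event-free for all 5 weeks and may also be replaced, and the sections that count to 38 treat such leavers differently

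*Protocol*

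**What the plan says.** **Who is analysed.** Protocol 9.4.2 puts the primary endpoint on the DLT analysis set. Table 16 (Protocol 9.3) admits a treated participant in one of two ways: by a DLT-like event, including one created by the composite intercurrent-event rule, or by at least 60% of the planned cumulative dose of both drugs "during the DLT-like assessment period, regardless of the completion in the DLT-like assessment period". SAP 8.1 has the same second criterion, with the percentage blacked out: "of xevinapant and cisplatin during the DLT-like assessment period, regardless of the completion in the DLT-like assessment period".

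**Who may be replaced.** Protocol 7.2, and 9.2 in the same terms: "Participants who prematurely discontinue, for reasons other than DLT-like events earlier than 5 weeks after start of treatment, may be replaced". Section 4.1 gives the purpose, which is to secure 38 evaluable participants in the DLT analysis set.

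**Who counts toward the 38.**
- Section 4.1: participants with an event, or with at least 60% dose who "either complete the DLT-like assessment period or discontinue study or study treatment for non-AE-related reasons".
- Section 4.4: 38 participants who "have completed the 5 weeks DLT-like assessment period or discontinued earlier and are not replaced". It sets no dose condition.
- Table 17 (Protocol 9.4.4): participants with an event, or with at least 60% dose who complete the period or leave the study, for whatever reason. SAP 6.2 has the same structure with the numbers blacked out.

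**The decision rule.** Protocol 9.2 calls treatment tolerable if the rate is below 40% both at the review with 18 participants and at the primary analysis. At 40% or more the SMC makes a recommendation from all available data.

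**The concern.** A non-event is a statement about the whole 5-week window. Table 16 accepts it from someone who was not watched for the whole window. An event counts as soon as it is seen, so for these participants shortened observation can only hide events. A death before Day 35 from a cause judged unrelated is the sharpest case: with dosing on schedule from Day 24, it enters as a full non-event.

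Replacement adds a second difficulty. It makes sense for people who fall outside the set, yet the visible text lets a leaver who is inside the set be replaced and removes nobody. Leaver and replacement can then both be in the denominator.

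Finally, Section 4.1 and the footnote to Table 15 treat the 38 as the DLT-evaluable participants. If the triggering count and the analysed set follow different rules, the number analysed need not be the number for which the 15-event limit was worked out.

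**Working it through.** **Inputs.** Cisplatin falls on Days 2, 9, 16, 23 and 30 of the first 35 days, and xevinapant on Days 1–14 and 22–35, which is 28 doses (Protocol 4.1). The limits are 7 of 18 and 15 of 38 (Protocol 9.2, Table 15). The documents do not give the number of early leavers, so it is assumed below.

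**1. The plan's own figures.** At a true rate of 0.30, the binomial P(X ≤ 7 | n = 18) = 85.9%, as stated ("the actual such probability at SMC with 18 participants is 85.9" per cent). For both looks, the sum over a = 0 to 7 of P(a | 18) × P(X ≤ 15 − a | 20) = 83.0%, as in Table 15.

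**2. Earliest day on which a leaver is kept as a non-event.** Cisplatin: 3/5 = 60% on Day 16. Xevinapant: 17/28 = 60.7% on Day 24 (16/28 = 57.1% on Day 23). A Day 24 leaver has missed 11/28 = 39.3%, just inside the composite rule's cut of more than 40%. The affected window is therefore about Days 24 to 34.

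**3. One case under each rule.** An on-schedule participant leaves the study on Day 28 because of an unrelated adverse event. They have had 21/28 = 75% of xevinapant and 4/5 = 80% of cisplatin, with no DLT-like event.
- Table 16 and SAP 8.1: in the analysis set, as a non-event.
- Section 4.1: not counted toward 38.
- Table 17: counted.
- Section 4.4: counted only if not replaced.

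Had the reason been unconnected with any adverse event, 4.1 would count the person too; 4.4 would still depend on replacement.

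**4. Chance of a hidden event in one leaver.** With constant hazard and a 30% risk over 35 days, the chance is 1 − 0.7^((35 − d)/35) for leaving on day d. This gives 10.6% at Day 24, 5.0% at Day 30, and an average of 5.9% over Days 24 to 34.

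**5. Effect on the rate.** Downward shift = f × p × r, where f is the share of such leavers, p the true rate and r the share of the 35-day risk that goes unobserved. Take f = 5% as an assumption, and r from 11/35 (even risk, leaving on Day 24) to 1 (upper bound).
- p = 0.30: 0.05 × 0.30 × 11/35 = 0.5 points, up to 1.5 points.
- p = 0.40: 0.6 points, up to 2.0 points. The chance of passing both looks rises from 42.8% to 45.6%, up to 51.8%.

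**6. Effect on the decision.** Take exactly one such leaver, outside the first 18. The result can change only if the other 37 have exactly 15 events, because 15/38 = 39.5% and 15/37 = 40.5%. The first look must also be passed: sum over a = 0 to 7 of P(a | 18) × P(15 − a | 19). If the leaver is replaced, the result changes only if the replacement has an event (16/38 = 42.1%), so that sum is multiplied by p.

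| True rate | Leaver dropped, not replaced | Leaver replaced |
|---|---|---|
| 30% | 2.9% | 2.9% × 0.30 = 0.9% |
| 35% | 5.8% | 5.8% × 0.35 = 2.0% |
| 40% | 7.3% | 7.3% × 0.40 = 2.9% |

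**7. The opposite effect.** If the same 5% instead left with less than 60% of dose, they would count as events. The shift is f × (1 − p) = +3.5 points at p = 0.30 and +3.0 points at p = 0.40.

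**The case against.** The strongest case on the other side is that the affected group is tiny and the plan covers most of it already.

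- **Stopping treatment is not leaving the study.** Protocol 7.1 keeps such participants in the study and 8.3 collects adverse events until end of study. This stands: only people who leave the study are truncated.
- **Treatment-related leavers are mostly caught.** Section 8.2.5.1 makes less than 60% of a cycle's dose, because of a treatment-related adverse event, a DLT-like event. In Cycle 2 that mark is passed only on Day 30 (9/14 xevinapant doses, 2/3 infusions). This stands too.
- **Unrelated death is observed to the end.** Calling it a tolerability non-event is a matter of definition. That is arguable, and is a reason to report such deaths separately.
- **Replacement is optional.** True, but nothing visible excludes a leaver who is already in the set.
- **Redaction and reduced scope.** SAP 9.11 (missing data) and 9.14 (assessment period) are blacked out and may deal with early leavers. SAP 7.1 cuts the work to the first SMC review and a synoptic report, whose list names no DLT-like table. Both limit the practical effect. The visible rule in SAP 8.1 and the analysis in SAP 15.1 remain.

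A reader might infer that the primary denominator is itself contradictory. It is not: it is defined once, in Table 16, and repeated in SAP 8.1. Sections 4.1, 4.4 and Table 17 set the cut-off or the completion date, and 4.1 and Table 17 ask for at least 38. The disagreement is over who counts toward that number.

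**Conclusion.** The point holds in a limited form. An event-free participant with at least 60% of both drugs who leaves the study on about Days 24 to 34 is analysed as a full non-event, may be replaced as well, and is counted toward the 38 in three different ways.

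Within that subgroup the error can only hide events. The size is about 0.5 to 2 points if 5% of participants are such leavers. The 5% is an assumption, and the lower end also assumes even risk over the window.

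A reader might infer that the trial's DLT-like rate is biased downward overall. The documents do not support this, because the composite rule turns lower-dose leavers into events and pushes the rate up. The net direction depends on when people leave, which is unknown.

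A reader might also infer that one leaver turns tolerable into not tolerable with probability 5.3%, 10.4% or 13.2% at true rates of 30%, 35% and 40%, the chance of exactly 15 events among 37. Those figures leave out the first look at 18 and the replacement; with both they are about 0.9%, 2.0% and 2.9%, still given that one such leaver exists. Nor does 40% or more produce a finding of intolerability: Protocol 9.2 sends it to a comprehensive SMC assessment.

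The change is still worth making, because it is a cheap correction to the analysis set of the only primary endpoint.

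**What to change.** Use one evaluability rule in Protocol 4.1, 4.4, Table 16 and Table 17, and in SAP 6.2 and 8.1. A participant is evaluable with either:

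- a DLT-like event, including one from the composite rule; or
- at least 60% of the planned dose of both drugs and adverse-event observation through Day 35, on or off treatment.

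State in 7.2 and 9.2 that event-free participants with at least 60% dose who leave the study before Day 35 are outside the denominator and are the ones who may be replaced. Report their number, and any deaths before Day 35, separately. Add a sensitivity analysis that counts them as events.

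The cost is wording in these places and possibly one or two more replacements. Excluding leavers conditions on completion, which can itself bias the rate if leaving is related to toxicity; the sensitivity analysis addresses that.
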